8.2. Analysis Methods

Descriptive statistics or frequency tabulations will be presented for all above parameters (except for the durations parameters) by treatment group.

A patient listing with details on the individual medical encounters will be created.

REFERENCES

2. Kliegman RM, Stanton B, St Geme J, Schor N, Behrman RE. *Nelson Textbook of Pediatrics*, 19th Edition.
3. Liptak, T. (1958). "On the combination of independent tests". *Magyar Tud. Akad. Mat. Kutato Int. Kozl.* 3: 171–197.

**ATTACHMENT 1. : LABORATORY: DIVISION OF MICROBIOLOGY AND
INFECTIOUS DISEASES (DMID) PEDIATRIC TOXICITY TABLES NOVEMBER 2007**

(Selected Values for children less than or equal to 3 months of age – does not apply to
preterm infants)

**For all parameters not listed in this table, please refer to
the DMID Toxicity Table for children >3 months of age**

HEMATOLOGY				
	Grade 1	Grade 2	Grade 3	Grade 4
Hemoglobin				
1-7 days old	13.0-14.0 g/dL	12.0-12.9 g/dL	<12 g/dL	Cardiac Failure secondary to Anemia
8-21 days old	12.0-13.0 g/dL	10.0-11.9 g/dL	<10.0 g/dL	Cardiac Failure secondary to Anemia
22-35 days old	9.5-10.5 g/dL	8.0-9.4 g/dL	<8.0 g/dL	Cardiac Failure secondary to Anemia
36-60 days old	8.5-9.4 g/dL	7.0-8.4 g/dL	<7.0 g/dL	Cardiac Failure secondary to Anemia
61-90 days old	9.0-9.9 g/dL	7.0-8.9 g/dL	<7.0 g/dL	Cardiac Failure secondary to Anemia
Absolute Neutrophil Count				
1 day old	5000-7000/mm ³	3000-4999/mm ³	1500-2999/mm ³	<1500/mm ³
2-6 days old	1750-2500/mm ³	1250-1749/mm ³	750-1249/mm ³	<750/mm ³
7-60 days old	1200-1800/mm ³	900-1199/mm ³	500-899/mm ³	<500/mm ³
61-90 days old	750-1200/mm ³	400-749/mm ³	250-399/mm ³	<250/mm ³

**DIVISION OF MICROBIOLOGY AND INFECTIOUS DISEASES (DMID)
PEDIATRIC TOXICITY TABLES NOVEMBER 2007**

(Selected values for children younger than or aged 3 months)

HEMATOLOGY (continued)				
	Grade 1	Grade 2	Grade 3	Grade 4
Bilirubin (fractionated bilirubin test must be performed when total bilirubin is elevated)				
<7 days old	-	20-25 mg/dL	26-30 mg/dL	>30 mg/dL
7-60 days old	1.1-1.9xN	2.0-2.9xN	3.0-7.5xN	>7.5xN
61-90 days old	1.1-1.9xN	2.0-2.9xN	3.0-7.5xN	>7.5xN
Creatinine				
<7 days old	1.0-1.7 mg/dL	1.8-2.4 mg/dL	2.5-3.0 mg/dL	>3.0 mg/dL
7-60 days old	0.5-0.9 mg/dL	1.0-1.4 mg/dL	1.5-2.0 mg/dL	>2.0 mg/dL
61-90 days old	0.6-0.8 mg/dL	0.9-1.1 mg/dL	1.2-1.5 mg/dL	>1.5 mg/dL
Creatinine Clearance				
<7 days old	35-40 mL/min	30-34 mL/min	25-29 mL/min	<25 mL/min
7-60 days old	45-50 mL/min	40-44 mL/min	35-39 mL/min	<35 mL/min
61-90 days old	60-75 mL/min	50-59 mL/min	35-49 mL/min	<35 mL/min
Hypocalcemia				
<7 days old	6.5-6.9 mEq/L	6.0-6.4 mEq/L	5.5-5.9 mEq/L	<5.5 mEq/L
7-60 days old	7.6-8.0 mEq/L	7.0-7.5 mEq/L	6.0-6.9 mEq/L	<6.0 mEq/L
61-90 days old	7.8-8.4 mEq/L	7.0-7.7 mEq/L	6.0-6.9 mEq/L	<6.0 mEq/L
Hypercalcemia				
<7 days old	12.0-12.4 mEq/L	12.5-12.9 mEq/L	13.0-13.5 mEq/L	>13.5 mEq/L
7-60 days old	10.5-11.2 mEq/L	11.3-11.9 mEq/L	12.0-13.0 mEq/L	>13.0 mEq/L
61-90 days old	10.5-11.2 mEq/L	11.3-11.9 mEq/L	12.0-13.0 mEq/L	>13.0 mEq/L

**DIVISION OF MICROBIOLOGY AND INFECTIOUS DISEASES (DMID)
PEDIATRIC TOXICITY TABLES NOVEMBER 2007**

(Older than 3 months of age)

HEMATOLOGY				
	Grade 1	Grade 2	Grade 3	Grade 4
Hemoglobin for children older than 3 months and younger than 2 years of age	9.0 - 9.9 g/dL	7.0 - 8.9 g/dL	<7.0 g/dL	Cardiac Failure secondary to anemia
Hemoglobin for children older than 2 years of age	10 - 10.9 g/dL	7.0 - 9.9 g/dL	<7.0 g/dL	Cardiac Failure secondary to anemia
Absolute Neutrophil Count	750 - 1200/mm ³	400 - 749/mm ³	250 - 399/mm ³	<250/mm ³
Platelets	-----	50,000 - 75,000/mm ³	25,000 - 49,999/mm ³	<25,000/mm ³
Prothrombin Time (PT)	1.1 - 1.2 x ULN	1.3 - 1.5 x ULN	1.6 - 3.0 x ULN	>3.0 x ULN
Partial Thromboplastin Time (PTT)	1.1 - 1.6 x ULN	1.7 - 2.3 x ULN	2.4 - 3.0 x ULN	>3.0 x ULN

GASTROINTESTINAL				
	Grade 1	Grade 2	Grade 3	Grade 4
Bilirubin (when accompanied by any increase in other liver function test)	1.1 - <1.25 x ULN	1.25 - <1.5 x ULN	1.5 - 1.75 x ULN	>1.75 x ULN
Bilirubin (when other liver function are in the normal range)	1.1 - <1.5 x ULN	1.5 - <2.0 x ULN	2.0 - 3.0 x ULN	>3.0 x ULN
AST (SGOT)	1.1 - <2.0 x ULN	2.0 - <3.0 x ULN	3.0 - 8.0 x ULN	>8 x ULN
ALT (SGPT)	1.1 - <2.0 x ULN	2.0 - <3.0 x ULN	3.0 - 8.0 x ULN	>8 x ULN
GGT	1.1 - <2.0 x ULN	2.0 - <3.0 x ULN	3.0 - 8.0 x ULN	>8 x ULN
Pancreatic Amylase	1.1 - 1.4 x ULN	1.5 - 1.9 x ULN	2.0 - 3.0 x ULN	>3.0 x ULN
Uric Acid	7.5 - 9.9 mg/dL	10 - 12.4 mg/dL	12.5 - 15.0 mg/dL	>15.0 mg/dL

**DIVISION OF MICROBIOLOGY AND INFECTIOUS DISEASES (DMID)
PEDIATRIC TOXICITY TABLES NOVEMBER 2007**

(Older than 3 months of age)

ELECTROLYTES				
	Grade 1	Grade 2	Grade 3	Grade 4
CREATININE				
3 months - 2 years of age	0.6 - 0.8 x ULN	0.9 - 1.1 x ULN	1.2 - 1.5 x ULN	>1.5 x ULN
2 years - 12 years of age	0.7 - 1.0 x ULN	1.1 - 1.6 x ULN	1.7 - 2.0 x ULN	>2.0 x ULN
Older than 12 years of age	1.0 - 1.7 x ULN	1.8 - 2.4 x ULN	2.5 - 3.5 x ULN	>3.5 x ULN
Hypernatremia	-	<145 - 149 mEq/L	150 - 155 mEq/L	>155 mEq/L or abnormal sodium AND mental status changes
Hyponatremia	-	130 - 135 mEq/L	129 - 124 mEq/L	<124 mEq/L or abnormal sodium AND mental status changes
Hyperkalemia	5.0 - 5.9 mEq/L	6.0 - 6.4 mEq/L	6.5 - 7.0 mEq/L	>7.0 mEq/L or abnormal potassium AND cardiac arrhythmia
Hypokalemia	3.0-3-5 mEq/L	2.5-2.9 mEq/L	2.0-2.4 mEq/L	<2.0 mEq/L or abnormal potassium AND cardiac arrhythmia
Hypercalcemia	10.5 - 11.2 mg/dL	11.3 - 11.9 mg/dL	12.0 - 12.9 mg/dL	>13.0 mg/dL
Hypocalcemia	7.8 - 8.4 mg/dL	7.0 - 7.7 mg/dL	6.0 - 6.9 mg/dL	<6.0 mg/dL
Hypomagnesemia	1.2 - 1.4 mEq/L	0.9 - 1.1 mEq/L	0.6 - 0.8 mEq/L	<0.6 mEq/L or abnormal magnesium AND cardiac arrhythmia
Hypoglycemia	55 - 65 mg/dL	40 - 54 mg/dL	30 - 39 mg/dL	<30 mg/dL or abnormal glucose AND mental status changes
Hyperglycemia	116 - 159 mg/dL	160 - 249 mg/dL	250 - 400 mg/dL	>400 mg/dL or ketoacidosis
Proteinuria	Tr-1+ or <150 mg/day	2+ or 150-499 mg/day	3+ or 500-1000 mg/day	4+ or Nephrotic syndrome >1000 mg/day
Hematuria	Microscopic <25 cells/hpf	Microscopic >25 cells/hpf	----	Gross hematuria

**DIVISION OF MICROBIOLOGY AND INFECTIOUS DISEASES (DMID)
PEDIATRIC TOXICITY TABLES NOVEMBER 2007**

(Older than 3 months of age)

ELECTROLYTES (continued)				
	Grade 1	Grade 2	Grade 3	Grade 4
Hypernatremia	-	<145 - 149 mEq/L	150 - 155 mEq/L	>155 mEq/L or abnormal sodium AND mental status changes
Hyponatremia	-	130 - 135 mEq/L	129 - 124 mEq/L	<124 mEq/L or abnormal sodium AND mental status changes
Hyperkalemia	5.0 - 5.9 mEq/L	6.0 - 6.4 mEq/L	6.5 - 7.0 mEq/L	>7.0 mEq/L or abnormal potassium AND cardiac arrhythmia
Hypokalemia	3.0 - 3.5 mEq/L	2.5 - 2.9 mEq/L	2.0 - 2.4 mEq/L	<2.0 mEq/L or abnormal potassium AND cardiac arrhythmia
Hypercalcemia	10.5 - 11.2 mg/dL	11.3 - 11.9 mg/dL	12.0 - 12.9 mg/dL	>13.0 mg/dL
Hypocalcemia	7.8 - 8.4 mg/dL	7.0 - 7.7 mg/dL	6.0 - 6.9 mg/dL	<6.0 mg/dL
Hypomagnesemia	1.2 - 1.4 mEq/L	0.9 - 1.1 mEq/L	0.6 - 0.8 mEq/L	<0.6 mEq/L or abnormal magnesium AND cardiac arrhythmia
Hypoglycemia	55 - 65 mg/dL	40 - 54 mg/dL	30 - 39 mg/dL	<30 mg/dL or abnormal glucose AND mental status changes
Hyperglycemia	116 - 159 mg/dL	160 - 249 mg/dL	250 - 400 mg/dL	>400 mg/dL or ketoacidosis
Proteinuria	Tr-1+ or <150 mg/day	2+ or 150-499 mg/day	3+ or 500-1000 mg/day	4+ or Nephrotic syndrome >1000 mg/day
Hematuria	Microscopic <25 cells/hpf	Microscopic >25 cells/hpf	-	Gross hematuria

**DIVISION OF MICROBIOLOGY AND INFECTIOUS DISEASES (DMID)
PEDIATRIC TOXICITY TABLES NOVEMBER 2007**

(Older than 3 months of age)

Drug Fever (Rectal)	-	38.5 - 40.0°C 101.3 - 104.0 °F	Greater than 40.0°C Greater than 104.0°F	Sustained Fever: Equal or greater than 40.0°C (104.0°F) for longer than 5 days
---------------------	---	-----------------------------------	---------------------------------------------------	-----------------------------------------------------------------------------------------------

ATTACHMENT 2. : VITAL SIGNS

The following classes for vital signs abnormalities will be defined based on the references [1] and [2], and internal pediatrician insight at J&J:

Parameter (unit)	Abnormality class	Age class				
		0 - 3 months	3 - 6 months	6 - 12 months	1 - 2-years	2- <3 years
Diastolic BP (mmHg)	abnormally low clinically relevant	<35	<40	<40	<40	<40
	abnormally low not clinically relevant	35 - <45	40 - <50	40 - <55	40 - <55	40 - <45
	Normal	45 - 55	50 - 65	55 - 65	55 - 70	45 - 60
	abnormally high not clinically relevant	>55 - 65	>65 - 85	>65 - 85	>70 - 90	>60 - 70
	abnormally high clinically relevant	>65	>85	>85	>90	>70
Systolic BP (mmHg)	abnormally low clinically relevant	<60	<60	<60	<75	<80
	abnormally low not clinically relevant	60 - <65	60 - <70	60 - <80	75 - <90	80 - <85
	Normal	65 - 85	70 - 80	80 - 100	90 - 105	85 - 100
	abnormally high not clinically relevant	>85 - 110	>80 - 110	>100 - 110	>105 - 120	>100 - 110
	abnormally high clinically relevant	>110	>110	>110	>120	>110
Heart rate HR (bpm)	abnormally low clinically relevant	<80	<70	<70	<60	<90
	abnormally low not clinically relevant	80 - <100	70 - <90	70 - <80	60 - <70	90 - <95
	Normal	100 - 150	90 - 120	80 - 120	70 - 110	95 - 125
	abnormally high not clinically relevant	>150 - 180	>120 - 150	>120 - 150	>110 - 140	>125 - 130
	abnormally high clinically relevant	>180	>150	>150	>140	>130
Respiratory rate	abnormally low clinically relevant	<25	<20	<20	<18	<20
	abnormally low not clinically relevant	25 - <35	20 - <30	20 - <25	18 - <20	20 - <22
	Normal	35 - 55	30 - 45	25 - 40	20 - 30	22 - 30
	abnormally high not clinically relevant	>55 - 70	>45 - 60	>40 - 60	>30 - 50	>30 - 35
	abnormally high clinically relevant	>70	>60	>60	>50	>35
Oxygen saturation SpO ₂ (%)	abnormally low clinically relevant	<92	<92	<92	<92	<92
	abnormally low not clinically relevant	92 - <96	92 - <96	92 - <96	92 - <96	92 - <96

Parameter	Abnormality class clinically relevant	Age class				
	Normal	≥96	≥96	≥96	≥96	≥96

ATTACHMENT 3. : ECG

The following classes for ECG abnormalities will be defined:

Parameter (unit)	Age class	Abnormally low	Abnormally high
PR (msec)	0 - 2 years	NA	>150
	2 - <3 years	<100	>150
QRS (msec)	0 - 2 years	NA	>79
	2 - <3 years	<40	>79
QT (msec) and QTc (msec)	0 - 2 years	NA	>500
	2 - <18 years	<320	>450
RR (msec)	0 - 3 months	<333	>750
	3 - 12 months	<400	>860
	1 - 2 years	<430	>1000
	2 - <18 years	<600	>1200

Criteria for Abnormal QTc Changes From Baseline		
	Classification	
QTc change from baseline	No concern	≤ 30
	Concern	$>30 - \leq 60$
	Clear concern	> 60
These criteria are based on the ICH E14 Guideline		

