The ECG variables that will be analyzed are heart rate, PR interval, QRS interval, QT interval, and QTcF.^{12,14,19} The percentage of subjects with abnormalities as defined in [Attachment 2](#) will be tabulated.

Vital Signs/SpO₂

Descriptive statistics of body temperature, heart rate, respiratory rate, SBP, DBP, SpO₂, and changes from baseline will be summarized at each scheduled timepoint. For SpO₂ an overview will be presented for the number of subjects (proportion) requiring supplemental oxygen. The percentage of subjects with values beyond clinically important limits, as judged by the investigator, will be summarized.

Physical Examination

Physical examination findings will be summarized at each scheduled timepoint. Descriptive statistics will be calculated at baseline and for observed values and changes from baseline at each scheduled timepoint. Frequency tabulations of the abnormalities will be made.

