Attachment 2: Cardiovascular Safety – Abnormalities

Electrocardiogram

All important abnormalities from the ECG readings will be listed.

Parameter (unit)	Age class	Abnormally low	Abnormally high
PR (msec)	0 - 2 years	NA	>150
	2 - <3 years	<100	>150
QRS (msec)	0 - 2 years	NA	>79
	2 - <3 years	<40	>79
QT (msec)	0 - 2 years	NA	>500
	2 - <18 years	<320	>450
RR (msec)	0 - 3 months	<333	>750
	3 - 12 months	<400	>860
	1 - 2 years	<430	>1000
	2 - <18 years	<600	>1200

Vital Signs

Normal ranges:

Parameter (unit)	Age class				
	0 - 3 months	3 - 6 months	6 - 12 months	1 - 2 years	2- <3 years
Diastolic BP (mmHg)	45 - 55	50 - 65	55 - 65	55 - 70	45 - 60
Systolic BP (mmHg)	65 -85	70 - 80	80 - 100	90 - 105	85 - 100
Heart rate HR (bpm)	100 - 150	90 - 120	80 - 120	70 - 110	95 - 125
Respiratory rate	35 - 55	30 - 45	25 - 40	20 - 30	22 - 30
Oxygen saturation SpO ₂ (%)	≥96	≥96	≥96	≥96	≥96

The following clinically relevant abnormalities will be defined for vital signs

Parameter (unit)		Age class			
		0 - 3 months	3 - 12 months	1 - 2-years	2- <3 years
Diastolic BP (mmHg)	abnormally low	<35	<40	<40	<40
	abnormally high	>65	>85	>90	>70
Systolic BP (mmHg)	abnormally low	<60	<60	<75	<80
	abnormally high	>110	>110	>120	>110
Heart rate HR (bpm)	abnormally low	<80	<70	<60	<90
	abnormally high	>180	>150	>140	>130
Respiratory rate	abnormally low	<25	<20	<18	<20
	abnormally high	>70	>60	>50	>35
Oxygen saturation SpO ₂ (%)	abnormally low	<92	<92	<92	<92

References: Normal ranges for vital signs based on the following references and internal pediatrician insight:

Kliegman RM, Stanton B, St Geme J, Schor N, Behrman RE. *Nelson Textbook of Pediatrics*, 19th Edition.

Attachment 3: Guideline for the Estimation of Glomerular Filtration Rate (GFR) Based on Serum Creatinine in Children

- The production of creatinine is proportional to muscle mass, which is in turn related to body mass and height (for normally proportioned individuals). Therefore in a steady-state situation the GFR can be estimated from the plasma creatinine according to Schwartz formula (for serum creatinine measured by Jaffe methodology):

$$\text{Children 1-12 years}^1: \quad e\text{GFR} = \frac{0.55 \times \text{length (cm)}}{\text{Serum creatinine (mg/dL)}}$$

- The Schwartz formula is modified for different age groups and sexes:

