LRTI	lower respiratory tract infection
MD	maintenance dose
PCR	polymerase chain reaction
PD	pharmacodynamic(s)
PK	pharmacokinetic(s)
popPK	population-derived pharmacokinetic(s)
PRESORS	Pediatric RSV Electronic Severity and Outcome Rating System
qRT-PCR	quantitative real-time reverse transcriptase-polymerase chain reaction
QTcF	QT interval corrected for heart rate according to Fridericia's formula
RBC	red blood cell
RNA	ribonucleic acid
RSV	respiratory syncytial virus
SAE	serious adverse event
SAP	statistical analysis plan
SBP	systolic blood pressure
SD	standard deviation
SpO ₂	peripheral capillary oxygen saturation
ULN	upper limit of normal
WBC	white blood cell

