6.5. Electrocardiogram

PR, QT, QRS, QTc intervals and heart rate will be investigated. QTcF values will be used as reported, they will not be recalculated.

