6.5.1. Definitions

The ECG abnormalities will be defined as indicated in [Attachment 3](#). In determining the abnormalities, the following rules are applied:

- Worst grades/abnormalities are determined over the whole observational period and for each trial phase separately, including post-baseline scheduled and unscheduled measurements of that phase.
- The abnormalities ‘abnormally low’ and ‘abnormally high’/grades are considered equally important, i.e. if a subject has as well an abnormally low as an abnormally high or graded value post-baseline, both abnormalities are shown in the tables. (This means that the sum of the percentages can be more than 100%)

An abnormality will be considered emergent in a particular phase if it is worse than baseline. If baseline is missing, the abnormality is always considered as emergent. A shift from ‘abnormally low’ at baseline to ‘abnormally high’ or ‘grade ...’ post baseline (or vice versa) is also emergent.

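### SAP Attachment 3 gives uncorrected QT and QTc the same absolute limits, so the QT limits are redundant under 2 years and flag normal QTc as low from 2 years, and the QTc limit changes at age 2 without a stated reason

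*SAP*

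**What the plan says.** SAP Section 6.5.1 takes its abnormality classes from the attachment ("The ECG abnormalities will be defined as indicated in" Attachment 3). There the two intervals share a row, labelled "QT (msec) and QTc (msec". It reads: "QT (msec) and QTc (msec) 0 - 2 years NA >500", followed by "2 - <18 years <320 >450". The columns after the age class are abnormally low and abnormally high, so under 2 years there is no low limit.

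Protocol Attachment 2 has the same numbers for uncorrected QT alone ("QT (msec) 0 - 2 years NA >500") and has no QTc limit of any kind. Yet protocol Section 11.8 treats the two as separate variables: "The ECG variables that will be analyzed are heart rate, PR interval, QRS interval, QT interval, and QTcF". It also says that abnormalities will be tabulated as protocol Attachment 2 defines them.

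SAP Attachment 3 has a second QTc criterion, which applies at every age. A change from baseline above 30 and up to 60 is a concern, and one above 60 is a clear concern. SAP Section 6.5.2 tabulates the worst QT/QTc change by treatment and phase. It also plans a cross-tabulation of worst abnormality against baseline, counts of emergent abnormalities, and a listing of abnormal values. On the source of the corrected interval, SAP Section 6.5 says: "QTcF values will be used as reported, they will not be recalculated".

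**The concern.** QT shortens as heart rate rises; QTc is meant to remove that dependence. One set of millisecond limits can suit both only near 60 bpm, where they coincide. The children in this trial have normal heart rates well above that, so one of the two variables must be misclassified.

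At stake is the meaning of a planned safety output. The worst-abnormality table, the emergent counts and the abnormal-value listing all use these classes. Under 2 years the QT cells will be almost empty by construction and could be read as reassurance. From 2 years the low-QT cells can fill with children whose corrected interval is unremarkable. The absolute QTc class also depends on which side of the second birthday a child falls: a QTc of 480 ms is unflagged at 23 months and abnormal at 25 months, although the measure is already rate-corrected. Only three ECGs are scheduled (screening, Day 4 or the day of earlier discharge, and Day 28), so the class given to each one matters.

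**Working it through.** **Inputs.** Normal heart rates come from SAP Attachment 2, the QT/QTc and RR limits from SAP Attachment 3, and the enrolment targets from SAP Section 1.2.1. QTc is taken to be QTcF, which the SAP abbreviations define as the "QT interval corrected for heart rate according to" Fridericia formula.

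**Formulas.** RR (ms) = 60,000 / heart rate. QTcF = QT / (RR in seconds)^(1/3).

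**Check against the plan's own figures.** The SAP's clinically relevant heart-rate limits reproduce its RR limits under 2 years: 180 and 80 bpm give 333 and 750 ms (0 to 3 months); 150 and 70 bpm give 400 and 857 ms (SAP 400 and 860, 3 to 12 months); 140 and 60 bpm give 429 and 1,000 ms (SAP 430 and 1,000, 1 to 2 years).

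**Step 1: what QT above 500 ms means under 2 years.** For example, at 100 bpm RR is 0.600 s, so QTcF = 500 / 0.600^(1/3) = 593 ms.

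| Age | Normal heart rate (bpm) | RR (ms) | QTcF when QT = 500 ms |
|---|---|---|---|
| 0–3 months | 100–150 | 600–400 | 593–679 |
| 3–6 months | 90–120 | 667–500 | 572–630 |
| 6–12 months | 80–120 | 750–500 | 550–630 |
| 1–2 years | 70–110 | 857–545 | 526–612 |

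QT of 500 ms equals QTcF of 500 ms only at 60 bpm (RR 1.000 s), below every normal range in the table. At any faster rate QTcF passes 500 ms first. From 120 bpm upward, a QT above 500 ms would exceed the whole RR interval.

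**Step 2: what the QT limits mean at 2 to under 3 years (95–125 bpm, RR 632–480 ms).**
- Low limit: 320 / 0.632^(1/3) = 373 ms at 95 bpm, and 320 / 0.480^(1/3) = 409 ms at 125 bpm. Any QTcF below that value gives a QT below 320 ms and a low flag, while the same row treats QTc from 320 to 450 ms as normal. A QTcF of 400 ms at 125 bpm is a QT of 400 × 0.480^(1/3) = 313 ms, which is flagged low.
- High limit: QT of 450 ms corresponds to QTcF of 524 ms at 95 bpm and 575 ms at 125 bpm, so this limit is redundant too.
- The neighbouring RR row has a similar mismatch. From 2 years RR below 600 ms is abnormal, which is any rate above 60,000 / 600 = 100 bpm, inside the SAP's normal 95–125 bpm.

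**Step 3: what escapes under 2 years.** A QTc of 451–500 ms is not in any absolute class. Reading the change classes in ms, it is also outside them only if the rise is 30 ms or less.

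| QTc on study (ms) | No concern if baseline is | Concern if baseline is | Clear concern if baseline is |
|---|---|---|---|
| 460 | 430 or more | 400 to under 430 | under 400 |
| 480 | 450 or more | 420 to under 450 | under 420 |
| 500 | 470 or more | 440 to under 470 | under 440 |

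With no baseline value the change cannot be calculated. SAP Section 6.5.1 foresees missing baselines.

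**Step 4: how many children.** The targets are at least 90 under 24 months, at least 12 from 24 to 36 months, and 120 to 180 in total. The under-2 share therefore runs from 90/180 = 50% to (180 − 12)/180 = 93%. At a total of 120 it runs from 90/120 = 75% to 108/120 = 90%.

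**The case against.** The strongest reply is that the SAP does look for QTc prolongation in infants. The change-from-baseline classes apply at all ages and are tabulated by arm and phase, next to summaries of actual values and mean plots. A drug effect would be expected to appear there, and a value already long before dosing says little about the drug. This stands, and it limits the consequence.

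Three stronger readings are tempting, and the documents do not support them.
- A reader might infer that a QTc of 451–500 ms under 2 years goes wholly unflagged, or that the plan cannot show a QT signal in infants. The change classes rule that out; the gap is confined to the absolute-value outputs.
- A reader might take 526–679 ms as the effective threshold under 2 years. It is not, because the same row applies 500 ms directly to QTc.
- A reader might suppose that the reported QTcF comes from each site's device and could be a Bazett value. The documents say only that it is used as reported, and they define it as Fridericia.

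Other points for the plan also have some force. Protocol Section 1.1.2 reports no potassium-channel blockage and no cardiovascular effects in dogs up to 500 mg/kg/day. Safety is descriptive, without testing. The low-QT problem affects only the older group (planned minimum 12), and a low value already present at baseline is not counted as emergent. Nothing in the documents establishes a normal infant QTc, so 450 ms cannot be called the correct limit for a one-month-old. Protocol Section 11 also leaves detail to the SAP. None of this explains why one row serves two different measurements or why the QTc limit moves at age 2.

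**Conclusion.** The concern holds in a limited form. The shared row does not work at the SAP's own normal heart rates. Under 2 years the QT limit is redundant, since it needs a QTcF of about 526–679 ms. At 2 to under 3 years the low QT limit marks as abnormal any QTcF below about 373–409 ms, against a stated normal QTc range of 320–450 ms. The step in the absolute QTc class from 500 to 450 ms at age 2 has no stated reason. It leaves QTc of 451–500 ms unflagged in the absolute-value table for about 50–93% of subjects. Within that group, a value escapes both criteria only when the rise is 30 ms or less or baseline is missing.

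This rests on reading QTc as QTcF, reading the change classes in ms, and using the SAP's normal heart-rate ranges; sick infants with faster rates would make the QT limit more remote still. The age share follows from enrolment targets, not from a fixed allocation. The primary endpoint, power and error control are not affected.

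**What to change.** In SAP Section 6.5 and Attachment 3:
- Give QT and QTc separate entries. Apply the absolute abnormality classes to QTcF only, and keep uncorrected QT as descriptive statistics.
- Tabulate QTcF above 450 ms and above 500 ms, both already in the table, as descriptive reporting classes at all ages, or state why the class should differ at age 2. These would be reporting categories, not clinical limits.
- Keep the change-from-baseline classes beside them, with their unit stated.
- Reconcile protocol Attachment 2, which has no QTc limit, with the SAP table, and say which one governs the tabulation promised in protocol Section 11.8. Protocol Section 9.7 also uses protocol Attachment 2 to decide which ECG abnormalities are recorded as adverse events, so the reconciliation should cover that use.

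Recalculating QTcF from the recorded QT and RR is an optional check on the reported values.

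The cost is a table edit and some SAP wording, plus a protocol clarification. The downside is some more flagged values under 2 years, in all arms; comparison with placebo puts them in context.
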